6.6 Baseline Definition

The Baseline visit (Day 0) will take place once the results of Screening assessments are obtained, suggesting that the subject is eligible for entering the study. During this visit, those subjects who qualify for entering the study will be randomized to one of the study arms in a ratio of 1:1.

6.7 Derived and Transformed Data

6.7.1 Baseline Age

Subject's age in years will be calculated based on the date of the Baseline Visit date using the following formula:

Age (years) = FLOOR ((INTCK ('month', Date of Birth, Date of Baseline Visit) - (DAY(Date of Baseline Visit) < MIN(DAY(Date of Birth), DAY (INTNX ('month', Date of Baseline Visit, 1) - 1))) /12)); where:

- FLOOR () is a SAS function that returns the largest integer that is less than or equal to the argument.
- INTCK () is a SAS function that returns the number of interval boundaries of a given kind that lie between two dates, times, or datetime values.
- DAY () is a SAS function that returns the day of the month from a SAS date value.
- INTNX () is a SAS function that increments a date, time, or datetime value by a given time interval, and returns a date, time, or datetime value.

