8.4 Sensitivity Analysis

A sensitivity analysis will be performed by Multiple Imputation Regression Analysis using the following factors: treatment, age, gender, race, baseline IGA, baseline CEA, baseline

PSA, smokers/non-smokers and the results of the same variable from previous visits. The Proc MI SAS code will be used to perform the analysis based on the mentioned factors.

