 Summary of Demographic and Baseline Characteristics
 mITT Population

Variable	Statistic	B244 Topical Spray n (%)	Placebo n (%)	All Patients n (%)
Age	N	xx	xx	xx
	Mean (SD)	xx.x (xx.xxx)	xx.x (xx.xxx)	xx.x (xx.xxx)
	Min, Max	xx.x, xx.x	xx.x, xx.x	xx.x, xx.x
Sex				
	Male	N (%) xx (xx.x)	xx (xx.x)	xx (xx.x)
	Female	N (%) xx (xx.x)	xx (xx.x)	xx (xx.x)
Ethnicity				
	Hispanic or Latino	N (%) xx (xx.x)	xx (xx.x)	xx (xx.x)
	Not Hispanic or Latino	N (%) xx (xx.x)	xx (xx.x)	xx (xx.x)
Race				
	American Indian or Alaskan Native	N (%) xx (xx.x)	xx (xx.x)	xx (xx.x)
	Asian	N (%) xx (xx.x)	xx (xx.x)	xx (xx.x)
	Black or African American	N (%) xx (xx.x)	xx (xx.x)	xx (xx.x)
	Native Hawaiian or Other Pacific Islander	N (%) xx (xx.x)	xx (xx.x)	xx (xx.x)

Protocol: RB244-001
 Confidential

STATISTICAL ANALYSIS PLAN

 Version 2
 02-Apr-19

Variable	Statistic	B244 Topical Spray n (%)	Placebo n (%)	All Patients n (%)
White	N (%)	xx (xx.x)	xx (xx.x)	xx (xx.x)
Other	N (%)	xx (xx.x)	xx (xx.x)	xx (xx.x)

NOTE: The percentages are based on the number of ITT Population.

Snapshot Data DD-MMM-YYYY

Program Name: <Pgm name>

Source: <Dataset>

Repeat for PP and Safety population

 Table 14.1.4.1
 Summary of Vital Signs,
 mITT Population

Visit	Vital Sign	Statistic	B244 Topical Spray n (%)	Placebo n (%)	All Patients n (%)	
Baseline	Height	N	xx	xx	xx	
		Mean (SD)	xx.x (xx.xxx)	xx.x (xx.xxx)	xx.x (xx.xxx)	
		CV	xx.x	xx.x	xx.x	
		Median	xx.x	xx.x	xx.x	
		Min, Max	xx.x, xx.x	xx.x, xx.x	xx.x, xx.x	
	Weight	N	xx	xx	xx	
		Mean (SD)	xx.x (xx.xxx)	xx.x (xx.xxx)	xx.x (xx.xxx)	
		CV	xx.x	xx.x	xx.x	
		Median	xx.x	xx.x	xx.x	
		Min, Max	xx.x, xx.x	xx.x, xx.x	xx.x, xx.x	
		Temperature	N	xx	xx	xx
			Mean (SD)	xx.x (xx.xxx)	xx.x (xx.xxx)	xx.x (xx.xxx)
	CV		xx.x	xx.x	xx.x	
	Median		xx.x	xx.x	xx.x	
	Min, Max		xx.x, xx.x	xx.x, xx.x	xx.x, xx.x	
	Heart Rate	N	xx	xx	xx	
		Mean (SD)	xx.x (xx.xxx)	xx.x (xx.xxx)	xx.x (xx.xxx)	
		CV	xx.x	xx.x	xx.x	
		Median	xx.x	xx.x	xx.x	
		Min, Max	xx.x, xx.x	xx.x, xx.x	xx.x, xx.x	
		Systolic BP	N	xx	xx	xx
Mean (SD)			xx.x (xx.xxx)	xx.x (xx.xxx)	xx.x (xx.xxx)	
CV	xx.x		xx.x	xx.x		
Median	xx.x		xx.x	xx.x		

Visit	Vital Sign	Statistic	B244 Topical	Placebo	All Patients	
			Spray n (%)	n (%)	n (%)	
Repeat for every visit showing Change from Baseline	Diastolic BP	CV	xx.x	xx.x	xx.x	
		Median	xx.x	xx.x	xx.x	
		Min, Max	xx.x, xx.x	xx.x, xx.x	xx.x, xx.x	
		N	xx	xx	xx	
		Mean (SD)	xx.x (xx.xxx)	xx.x (xx.xxx)	(xx.xxx)	
		CV	xx.x	xx.x	xx.x	
		Median	xx.x	xx.x	xx.x	

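### The SAP's formula for age in years has a misplaced bracket and, as printed, returns completed months, about 12 times the true age

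*SAP*

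**What the plan says.** SAP v2.0 section 6.7.1 (Baseline Age) states its purpose plainly: "Subject's age in years will be calculated based on the date of the Baseline Visit date using the following formula". The expression opens "Age (years) = FLOOR ((INTCK ('month', Date of Birth, Date of Baseline Visit". After a closing bracket, a minus sign and an opening bracket it continues "DAY(Date of Baseline Visit) < MIN(DAY(Date of Birth), DAY (INTNX ('month', Date of Baseline Visit, 1) - 1))) /12", and two more closing brackets end it. The part that matters here is the stretch "Date of Baseline Visit, 1) - 1))) /12", where three brackets close before the division. The section then explains the functions: "FLOOR () is a SAS function that returns the largest integer that is less than or equal to the argument", and "INTCK () is a SAS function that returns the number of interval boundaries of a given kind that lie between two dates, times, or datetime values". Section 6.7.1 of SAP v1.0 prints the same expression with the same brackets.

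Age appears in two places in the analysis. Section 7.3 lists it among the baseline data to be tabulated, and section 10.1.1 plans "Summary of Demographic and Baseline Characteristics" for the mITT, PP and Safety populations (Tables 14.1.3.1, 14.1.3.2 and 14.1.3.3). Section 8.4 names it among the multiple imputation factors, in the list beginning "treatment, age, gender, race, baseline IGA".

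Section 5.1 says that the final analysis follows the SAP. Section 6.4 says that true differences in analysis methods or data handling have to be documented.

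**The concern.** The label promises years, but the division by 12 that should turn months into years does not act on the month count. The expression is balanced and should run in SAS without a syntax error, so nothing in the program itself would flag it. A programmer who follows it produces ages in the hundreds. One who silently corrects it runs a derivation that differs from the approved SAP. At stake is the correctness of one descriptive baseline variable in three tables, and agreement between the SAP and the code.

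**Working it through.** **Inputs.** All come from SAP v2.0 section 6.7.1. Write DOB for the date of birth and V for the Baseline Visit date. Let

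- M = INTCK('month', DOB, V), the number of month boundaries between the two dates;
- B = the comparison DAY(V) < MIN(DAY(DOB), last day of V's month), which SAS evaluates as 1 if true and 0 if false.

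**Bracket count.** In this shorthand the printed expression is

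`FLOOR((INTCK('month',DOB,V) - (DAY(V) < MIN(DAY(DOB), DAY(INTNX('month',V,1) - 1))) /12))`

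There are 9 opening and 9 closing brackets, so it is balanced. Bracket depth runs as follows:

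1. FLOOR opens depth 1 and the bare bracket opens depth 2.
2. INTCK opens depth 3 and closes back to 2.
3. The comparison opens depth 3. Inside it, DAY(V) opens and closes, MIN opens depth 4, DAY(DOB) opens and closes, the last DAY opens depth 5, and INTNX opens and closes.
4. The three brackets after the final `- 1` close that DAY (to 4), MIN (to 3) and the comparison (to 2).
5. The `/12` therefore stands at depth 2, beside INTCK. Division precedes subtraction, so it acts only on the closed comparison.

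**What the expression returns.**

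- As printed: FLOOR(M − B/12). If B = 0 this is M. If B = 1 it is FLOOR(M − 1/12) = M − 1. In both cases it equals M − B, which is completed months.
- As intended: FLOOR((M − B)/12), which is completed years.

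**Worked cases.** The dates are assumed, since the documents give no subject dates.

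| Born | Baseline | M | B | As printed | Intended |
|---|---|---|---|---|---|
| 20 Jun 1973 | 10 Sep 2018 | 45×12 + 3 = 543 | 1 (10 < 20) | 542 | FLOOR(542/12) = 45 |
| 20 Jun 1974 | 10 Sep 2018 | 531 | 1 | 530 | 44 |
| 10 Sep 1978 | 10 Sep 2018 | 480 | 0 | 480 | 40 |
| 10 Sep 2000 | 10 Sep 2018 | 216 | 0 | 216 | 18 |
| 11 Sep 1948 | 10 Sep 2018 | 840 | 1 | 839 | 69 |

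**Size of the error.** A subject aged y completed years has between 12y and 12y + 11 completed months, so the ratio of printed result to true age lies between 12 and 12 + 11/y. At the youngest eligible age, y = 18, the upper end is 12 + 11/18 = 12.61. In 200,000 simulated date pairs (ages about 18 to 80, visits in the second half of 2018, both assumed) the ratio ran from 12.0 to 12.61, with a mean of 12.13.

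**Check of the correction.** FLOOR((M − B)/12) equalled completed years in all 200,000 pairs. The simulation had no February visits. For someone born on 29 February and seen on 28 February of a non-leap year, B = 0 (28 is not below MIN(29, 28)), so the birthday counts as reached. That is a convention set by the MIN term and not part of this error.

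**The case against.** **This is a typing slip that will correct itself.** The intent is unmistakable: both the sentence and the label say years, and the table shell allows two digits before the decimal point. Any adult would show a value of 216 or more, which a table reviewer would probably notice. This stands, and it is why the point is of low severity. It does not remove the point, because the section is an operative derivation rule and the expression passed unchanged from v1.0 to v2.0.

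**It may be a PDF reading error.** That is unlikely. The brackets balance, and the same string appears separately in both SAP versions. As printed, the bare bracket after FLOOR encloses the whole argument and does nothing. It has a purpose only if it closes before the division.

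**Stronger readings that the documents do not support.**

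- *Under-age subjects could enter or go unrecognised.* A reader might infer this from the 18-year limit in Protocol section 5.1.1. But sites check eligibility at Screening and Baseline (Protocol Table 1), with date of birth recorded at Screening (Protocol section 11.1.1). The SAP's list of unmet entry criteria (section 7.1) and its PP definition (section 6.5.4) do not refer to the derived age.
- *The sensitivity analysis is distorted.* Age is an imputation factor, but completed months equal 12 times completed years plus 0 to 11. This is close to a linear rescaling, so the coefficient changes scale and the imputed values should hardly move.
- *Reported ages are wrong.* The documents show a wrong instruction. They do not show how it was programmed.

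**Conclusion.** The expression in section 6.7.1 is wrong as printed: it yields completed months under a label of years. If programmed as written, every age in Tables 14.1.3.1 to 14.1.3.3 would be 12 to about 12.6 times too large for subjects aged 18 and over. The effect stops at those descriptive rows. The efficacy tests in section 8.3, the safety analysis in section 8.2 and the sample size in section 8.1 do not use age, and the imputation in section 8.4 would be essentially unchanged. The conclusion rests on standard SAS operator precedence and on the printed brackets. The assumed dates serve only to illustrate it. Section 9 of the SAP cites a paper on calculating age in one line of code, which was not available, so whether the slip arose in transcription cannot be said.

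**What to change.** In section 6.7.1, move one closing bracket from after the 12 to before the division sign, so that the month count less the comparison is closed before it is divided. In the shorthand above:

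`Age (years) = FLOOR((INTCK('month',DOB,V) - (DAY(V) < MIN(DAY(DOB), DAY(INTNX('month',V,1) - 1))))/12)`

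The brackets still balance, at nine of each. The cost is one character moved in the SAP text, or a short documented correction if the SAP is not reissued, plus a check that the program producing Tables 14.1.3.1 to 14.1.3.3 uses the corrected form. No design, data collection or other analysis changes.

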6.7.2 Study Day

Day 1 is defined as the day after the baseline when the subject will receive the first dose.

- For a visit date on or after the date of the first dose:
Study Day = (date of interest – date of first dose) + 1
- For a visit date before the date of the first dose:
Study Day = (date of interest – date of first dose)

6.7.3 Multiple Assessments

No multiple assessment for same visit are scheduled.

6.7.4 Handling of Missing Data & Sensitivity Analysis

For the primary and secondary analysis no missing values will be imputed. A sensitivity analysis will be performed by Multiple Imputation Regression Analysis using the following factors: treatment, age, gender, race, baseline IGA, baseline CEA, baseline PSA, smokers/non-smokers and the results of the same variable from previous visits.

6.7.5 Missing Start and Stop Dates for Prior and Concomitant Medication

Start date:

- If start date is completely missing, start date will not be imputed.
- If (year is present, and month and day are missing) or (year and day are present, and month is missing), set month and day to January 1.
- If year and month are present and day is missing, set day to the 1st day of month.

Stop date:

- If end date is completely missing, end date will not be imputed.
- If (year is present, and month and day are missing) or (year and day are present, and month is missing), set month and day to December 31st.
- If year and month are present and day is missing, set day to the last day of month.

6.7.6 Safety Parameters

Safety and tolerability endpoints will consist of all adverse events (AEs) reported during the study duration from the date of randomization through Week 12 (End of Study Visit).

Specific AEs are defined below.

Treatment-Emergent Adverse Events (TEAE): Any AE with onset after the first dose of study medication through 56 days after the last dose of study medication.

Serious Adverse Event (SAE): An AE occurring at any dose that results in any of the following outcomes: death, a life-threatening AE, in-patient hospitalization or prolongation of existing hospitalization, a persistent or significant disability/incapacity, or a congenital anomaly/birth defect.

Associated with Use of the Study Drug: There is a reasonable possibility that the experience may have been caused by the study drug. If the Investigator does not know whether or not study drug caused the event, then the event will be handled as “related to study drug” for reporting purposes. The determination of whether an AE is related to study drug is as follows:

- Related: The AE has a missing, unknown, possible, probable or definite relationship to the study medication.
- Not related: The AE is unlikely or definitely unrelated to the study drug.

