12.1.2 Serious Adverse Events

If an AE meets any of the following criteria, it is to be reported to the Sponsor’s Safety department and Pharmacovigilance as a Serious Adverse Event (SAE) using SAE report form within 24 hours of occurrence or notification to the study site:

Death of Subject	An event that results in the death of a subject.
Life-Threatening	An event that, in the opinion of the Investigator, would have resulted in immediate fatality if medical intervention had not been

	taken. This does not include an event that would have been fatal if it had occurred in a more severe form.
Hospitalization	An event that results in an admission to the hospital for any length of time. This does not include an emergency room visit or admission to an out-patient facility.
Prolongation of Hospitalization	An event that occurs while the study subject is hospitalized and prolongs the subject's hospital stay.
Congenital Anomaly/birth defect	An anomaly detected at or after birth or any anomaly that result in fetal loss.
Persistent or Significant Disability/Incapacity	An event that results in a condition that substantially interferes with the activities of daily living of a study subject. Disability is not intended to include experiences of relatively minor medical significance such as headache, nausea, vomiting, diarrhea, influenza, and accidental trauma (e.g., sprained ankle).
Other Important Medical Event	An important medical event that may not be immediately life-threatening or result in death or hospitalization, but based on medical judgment may jeopardize the subject and may require medical or surgical intervention to prevent any of the outcomes listed above (i.e., death of subject, life-threatening, hospitalization, prolongation of hospitalization, congenital anomaly, or persistent or significant disability/incapacity). Examples of such events include allergic bronchospasm requiring intensive treatment in an emergency room or at home, blood dyscrasias or convulsions that do not result in inpatient hospitalization, or the development of drug dependency or drug abuse.

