Withdrawal and Early Discontinuation	A subject may voluntarily withdraw from the study at any time and for any reason without prejudice to his or her future medical care. The Investigator, Sponsor, or Medical Monitor may also withdraw a subject at any time if it is medically necessary or in the interest of subject's safety. If a subject discontinues prematurely, the Investigator will perform Early Termination (ET) visit, capturing the reason for discontinuation. Further details are provided in section 5.2 & 5.3 of the Protocol RB244-001 v4.0.	
Prohibited Concomitant Medication	Prohibited Therapies are those medicinal products and treatment methods that are not allowed during the study period and within the timeframes specified in the section 8.1 of the Protocol RB244-001 v 4.0.	
Study Drug	Study drug includes Test and Placebo drug products. The Sponsor will supply study drug as matching 30ml/bottle, labeled for a blinded study. 
 • Test Drug: B244, 30ml/bottle (AOBiome, LLC) • Placebo: Vehicle, 30ml/bottle (AOBiome, LLC) 	

Duration of Patient Study Participation	Up to 84 ± 2 days
Study Endpoints	
PRIMARY
 
 The primary safety endpoint is to assess the safety and tolerability of B244 applied twice daily (BID) to the face for 8 weeks in subjects with mild to moderate rosacea based on the number of AE & SAE. 
EXPLORATORY
 
To assess the efficacy of B244 in subjects with mild to moderate rosacea.
 
 Change of IGA score at Baseline to Week 1, Week 4, Week 8 and Week 12 Change of CEA score at Baseline to Week 1, Week 4, Week 8 and Week 12. Change of PSA score at Baseline to Week 1, Week 4, Week 8 and Week 12. Change of Skindex 16 patient reported outcome from Baseline to Week 1, Week 4, Week 8 and Week 12 IGA treatment success, defined as “clear” or “almost clear” with a 2-grade improvement in IGA score from baseline to the end of treatment. CEA treatment success, defined as “clear” or “almost clear” with a 2-grade improvement in CEA score from baseline to the end of treatment

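### SAP 6.7.6 leaves the protocol's Other Important Medical Event criterion out of its SAE definition, so SAEs can be undercounted if it is applied as written

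*SAP*

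**What the plan says.** Protocol section 12.1.2 sets the rule for sites. It opens "If an AE meets any of the following criteria, it is to be reported to the" sponsor's safety function as an SAE within 24 hours, and then lists seven criteria. The last, Other Important Medical Event, begins "An important medical event that may not be immediately life-threatening or result in death or hospitalization". One of its examples is "allergic bronchospasm requiring intensive treatment in an emergency room or at home"; blood dyscrasias and convulsions without inpatient admission are others. On the hospitalization criterion the same section adds: "This does not include an emergency room visit or admission to an out-patient facility".

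SAP version 2, section 6.7.6, does not point to that list. It gives its own definition, which starts "Serious Adverse Event (SAE): An AE occurring at any dose that results in any of the following outcomes: death, a life-threatening AE" and finishes "in-patient hospitalization or prolongation of existing hospitalization, a persistent or significant disability/incapacity, or a congenital anomaly/birth defect". Version 1 of the SAP has the same text.

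The SAP version 2 synopsis, under Study Endpoints, describes the primary safety endpoint as "based on the number of AE & SAE". Section 8.2.1 names SAEs among the safety variables, next to AEs, vital signs and laboratory data. Sections 3.2.1 and 6.7.6 describe the endpoint as all adverse events.

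**The concern.** The two documents use different definitions of the same term. The site classifies seriousness on seven criteria, while the SAP defines it for analysis on six. The SAP's list is closed: it contains no open-ended wording and no reference to the protocol.

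Safety and tolerability is the only primary objective. SAEs have their own table (14.3.2), the TESAE rows of Table 14.3.1 and their own listing (16.2.3.2). An event reported on an SAE form could lose its seriousness classification in the study report, and the SAE count there would then not reconcile with the reports held by the sponsor's safety team. SAEs are likely to be few in a trial of this size, so a single reclassified event could change what a reader takes from the table.

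**Working it through.** The plan states no figure that bears on this point, so the check is a comparison of the two texts.

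| Criterion | Protocol 12.1.2 | SAP v2 6.7.6 |
|---|---|---|
| Death | yes | yes |
| Life-threatening | yes | yes |
| Hospitalization | yes | yes |
| Prolonged hospitalization | yes | yes |
| Congenital anomaly or birth defect | yes | yes |
| Disability or incapacity | yes | yes |
| Other Important Medical Event | yes | **no** |

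Protocol: 7 criteria. SAP: 6 of those 7 (the two hospitalization criteria share one phrase).

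**Which events fall in the gap.** An event is affected only if it meets the seventh criterion and none of the other six. The protocol's own examples show that such events can exist. Bronchospasm treated in an emergency room or at home involves no admission, and the protocol does not count an emergency-room visit as hospitalization. If the event is also not life-threatening, disabling or fatal, it is an SAE for the site and not one under 6.7.6. Convulsions without admission are in the same position.

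**Whether another part of the SAP closes the gap.** Section 2 refers the reader to the protocol and eCRFs, but for study conduct and data collection, not for definitions used in analysis. Section 5.1 says the final analysis follows the SAP's instructions. No section says that the protocol definition, or the site's seriousness classification, determines what enters the SAE tables.

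**Size.** The documents give no expected SAE rate and no share of SAEs that would qualify on the seventh criterion alone. The undercount therefore lies between zero and the number of SAEs that qualify only on that criterion. For illustration, assume that all of the approximately 130 planned subjects are treated, in a 1:1 ratio, and that one event in one arm is omitted:

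- subjects per arm: 130 / 2 = 65
- with the event counted: 1/65 = 1.5%
- with the event omitted: 0/65 = 0%

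The single event is an assumption, not a forecast. I give no confidence intervals, because the safety reporting is descriptive and the safety table shells show counts and percentages only.

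**The case against.** The strongest reply is that the gap may never matter in practice. The site judges seriousness under the protocol, and protocol section 12.5 makes the seriousness criteria a minimum field of the SAE report. Nothing in the SAP tells a programmer to downgrade an event that a site reported as serious. If the SAE tables are built from the site's classification, nothing is lost. This stands, and it makes the consequence conditional. It does not remove the problem, because the only definition the SAP states is the narrower one, and the SAP does not say that the site's classification overrides it.

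Three stronger readings are tempting, and the documents do not support them.

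- A reader might infer that a severe reaction treated in an emergency room is an SAE only through the missing criterion. Both documents keep the life-threatening criterion, which requires no admission, so the most dangerous reactions of this kind remain SAEs under the SAP.
- A reader might infer that the SAE count is the primary safety endpoint, or that affected events vanish from the safety analysis. AEs are part of the endpoint wherever it is described. An affected event, where treatment-emergent, stays in Tables 14.3.1 to 14.3.1.3 and in Listing 16.2.3.1 with its severity and relationship.
- A reader might take the exclusion of subjects with known sensitivity to B244 as evidence that hypersensitivity is an identified risk. It is an eligibility criterion. The protocol's background describes the health risk as minimal and reports no attributable drug-related SAEs in the two completed acne trials.

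**Conclusion.** The SAP's SAE definition is wrong as written: it contradicts protocol 12.1.2 by omitting one of seven criteria, and no other part of the SAP repairs it. Applied literally, it can only lower the SAE and TESAE counts, and it can make them disagree with the sponsor's SAE reports. The effect is limited to events that qualify solely as important medical events, and to the case in which 6.7.6 rather than the site's classification drives the tables. These events would still be reported as AEs. The number affected cannot be derived from the documents and may be zero, so it should not be inferred that SAEs will in fact be undercounted. Sample size and power are not involved. The point is worth correcting because it concerns a component of the primary safety endpoint and the definition should not be left to programming choice.

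**What to change.** In SAP section 6.7.6, replace the SAE sentence with the protocol 12.1.2 definition, including Other Important Medical Event, or with a cross-reference to that section. Add a statement that every event reported as serious under protocol 12.1.2 counts as an SAE in Table 14.3.2 and Listing 16.2.3.2 and, where treatment-emergent, in the TESAE rows of Table 14.3.1. This also settles which classification drives those outputs.

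The cost is a short text change to the SAP. It needs no new data and no change to site reporting. Compared with 6.7.6 as written, the SAE count can only stay the same or rise.
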